6.6 ECG

The ECG data includes quantitative variables such as ventricular rate, PQ or PR interval, R-R interval, QRS duration, and uncorrected QT interval as well as categorical variables such as ECG interpretation (normal or abnormal), ECG evaluation type (rhythm, conduction, etc) and ECG findings (prolonged QTc, low voltage, etc).

6.6.1 Corrected QT interval

The QT interval data will be corrected according to the Bazett and Fridericia formulas. The Bazett formula corrects the QT interval by dividing by the square root of the R-R interval (secs). The Fridericia formula corrects the QT interval by dividing by the cubic root of the R-R interval (secs). Maximum increase in corrected QT interval from baseline will be used to summarize the frequencies of subjects who fulfill the abnormality criteria based on the corrected QT interval will be calculated.

6.6.2 Abnormality criteria for corrected QT interval

Abnormality criteria for the corrected QT interval (Bazett and Fridericia) are listed in Table 6-4.

Table 6-4 Abnormality criteria for corrected QT interval

	Male Patients	Female Patients
1	>450 msec	>460 msec
2	>500 msec	>500 msec
3	30 - 60 msec increase from Baseline	
4	>60 msec increase from Baseline	

6.6.3 ECG findings

ECG findings are associated with the ECG evaluation type and thus abnormal findings will be summarized by the ECG evaluation type.

6.6.4 Data summaries

Summaries on the SAF set by treatment group include:

- Summary statistics and changes from baseline in quantitative ECG parameters by visit
- Incidence rates of abnormal corrected QT interval (Bazett and Fridericia) as defined by the abnormality criteria in Table 6-4
- Frequency (%) distribution of ECG findings by ECG evaluation type by visit

For non by-visit summaries, visits defined by visit-windows will not be used. All available data from scheduled and unscheduled visits will be considered.

6.7 First dose (second dose/restart dose/dose increase) monitoring

6.7.1 Vital signs

Hourly vital signs including pulse, SBP and DBP are collected for the first dose, second dose (if necessary), dose increase (if applicable), and restarting of dose after interruption (if applicable). The bradycardia events, bradycardia symptoms, and bradycardia treatment during first and second dose monitoring will be collected and summarized as well.

6.7.2 ECG

ECG will be performed at pre-dose, 6 hours post dose, and >6 hours post dose during the first dose, second dose (if necessary), dose increase (if applicable), and restarting of dose after interruption (if applicable).

6.7.3 Dose monitoring experience

The overall dose monitoring experience refers to the information collected on the dose administration monitoring eCRFs (e.g., whether subjects are discharged after 6 hours post-dose or extended monitoring is required after 6 hours post-dose, whether subjects are hospitalized, whether subjects discontinue the study drug permanently, and whether SAE is reported, etc.). All data with yes/no responses will be summarized.

6.7.4 Data summaries

Summaries on the safety set by treatment group include:

- Summary statistics and changes from pre-dose in vital signs by hour (1st dose, 2nd dose, dose increase, and restarts)
- Frequency (%) distribution of categorized sitting pulse or change (or percent change) from pre-dose sitting pulse during first dose administration (note that categories are given in table shells)

- Summary of the overall dose monitoring experience (1st dose, 2nd dose, dose increase, and restarts)
- Incidence of bradycardia events (1st dose and 2nd dose)
- Incidence of medications used for bradycardia (1st dose and 2nd dose)
- Incidence of bradycardia symptoms by SOC, PT, and severity (1st and 2nd dose)
- Incidence of notable vital sign abnormalities based on the notable criteria in Table 6-1 (1st dose and 2nd dose)
- Summary statistics and changes from pre-dose in ECG parameters by time point during 1st and 2nd dose administration
- Incidence of abnormal QTc interval (Bazett and Fridericia) as defined by the abnormality criteria in Table 6-4 during 1st and 2nd dose administration
- Frequency (%) distribution of ECG findings by ECG evaluation type by time point during 1st and 2nd dose administration

Plots on the SAF set by treatment group include:

- Box and whisker plot of vital signs during 6 hours post first dose administration

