- Heart rate (sitting) at discharge must not be the lowest hourly value measured during the observation period (which would be suggestive of a continuing progressive decline in heart rate)
- Patients must have no symptoms in sitting or standing position associated with decreased heart rate or received treatment for bradycardia
- ECG at 6 hours should not show any new significant abnormalities, other than asymptomatic sinus bradycardia, not observed at the patient's pre-dose ECG (e.g. prolongation of QT/QTcF interval, persistent new onset 2nd degree (Mobitz Type I (Wenkebach) or higher AV block, 3rd degree AV block at any time during monitoring).

The same monitoring procedure applies also to the re-initiation of study drug after interruption ([Section 5.5.5](#)) and at the time of individual dose-increase ([Section 3.3](#)). In the Core Phase, re-initiation of study drug monitoring must be done by the independent first dose monitoring team in order to maintain the blind. However, in the Extension Phase monitoring for re-initiation of study drug or dose increases may be conducted by the main study team.

Patients who are off study drug treatment for the following durations:

- The treatment lasted for 14 days or less and was interrupted for 1 day or more, or
- The treatment lasted for more than 14 days and less than 29 days and was interrupted for more than 7 consecutive days, or
- The treatment lasted for 4 weeks or more and was interrupted for more than 14 consecutive days.

Patients should have written instruction on when to return to the clinic and a 24 hour contact phone number to call in the event of any new or warranted symptoms (chest pain, dizziness, palpitations, syncope, nausea, vomiting, etc.).

If the above discharge criteria are not met, patients should continue to be observed until they are met (the observation must last for at least 2 hours even if the criteria are met earlier).

However, patients experiencing any symptomatic event associated with reduction of the heart rate, a heart rate of < 45 bpm at the end of the 6-hour monitoring, received treatment for bradycardia, or had relevant changes on the ECG, not resolving by the end of the 6-hour monitoring (e.g. ECG at 6 hours shows a QTcF interval ≥ 500 msec), must be hospitalized overnight. For those patients, the Day 2 dose of study drug should be given in the hospital according to monitoring and discharge criteria described above.

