3.8.4.2 Visits windows

For data not listed in [Section 3.8.4.1](#), visit-windows will be defined and used for the by-visit summaries. Visit-windows will only be defined for post-baseline visits and applied to post-baseline data (including both scheduled and unscheduled visit). Based on the study assessment schedule as specified in the study protocol, visit-windows are defined by a set of days around each nominal visit target day.

Visit-windows for vital signs, laboratory assessments, ophthalmologic examination (excluding OCT), pulmonary function tests, and ECG are provided in Table 3-4 to Table 3-9. These visit-windows will not be applied to any data related to the first dose or second dose or restart dose monitoring which will be summarized separately.

When visit-windows are used, all post-baseline visits will be re-aligned, i.e., they will be mapped into one of the visit-windows. E.g., if a subject's *Month 1* visit is delayed and occurs on Day 47, then it will be re-aligned to visit-window *Month 2*. As a result, it is possible that several assessments may fall into one particular visit-window. Statistical approaches to handle multiple visits in a given visit-window are described in [Section 3.8.6](#). Tables displaying summary statistics "by visit" will also use the term visit-window as column header; this is to remind the reviewer that multiple assessments of a subject might be summarized.

Table 3-4 Visit-windows for vital signs, physical development, and laboratory values (hematology/blood chemistry other than liver panel)

Visit	Start day	Target Day	End day
Week 2	1	14	22
Month 1	23	30	45
Month 2	46	60	75
Month 3	76	90	135
Month 6	136	180	225
Month 9	226	270	315
Month 12	316	360	405
Month 15	406	450	495
Month 18	496	540	585
Month 21	586	630	675
Month 24	676	720	765

Table 3-5 Visit-windows for urinalysis

Visit	Start day	Target Day	End day
Month 6	1	180	270
Month 12	271	360	540
Month 24	541	720	765

Table 3-6 Visit-windows for liver panel

Visit	Start day	Target Day	End day
Week 2	1	14	22
Month 1	23	30	37
Month 1.5	38	45	52
Month 2	53	60	75
Month 3	76	90	105
Month 4	106	120	135
Month 5	136	150	165
Month 6	166	180	225
Month 9	226	270	315
Month 12	316	360	405
Month 15	406	450	495
Month 18	496	540	585
Month 21	586	630	675
Month 24	676	720	765

Table 3-7 Visit-windows for ophthalmologic examination (excluding OCT)

Visit	Start day	Target Day	End day
Month 3	1	90	135
Month 6	136	180	225
Month 9*	226	270	315
Month 12*	316	360	450

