6.4.3 Data summaries

The following summaries will exclude hourly vital sign data from the first dose or second dose or restart dose monitoring (first dose data discussed in Section 6.7.1).

Summaries on the SAF set by treatment group include:

- Summary statistics and changes from baseline in vital sign parameters by visit
- Frequency (%) distributions of highest SBP, DBP, and lowest pulse in pre-defined categories respectively (as specified in the table shell);
- Incidence of notable vital sign abnormalities based on the notable criteria in Table 6-1

Summaries on the FUS by treatment group include:

- Incidence of notable vital sign abnormalities based on the notable criteria in Table 6-1 will be summarized by time-window (days 1 to 45 after study drug discontinuation, and more than 45 days after study drug discontinuation)

Plots on the SAF set by treatment group include:

- Box and whisker plot of vital signs by visit

Table 6-1 Criteria for clinically notable vital signs

Vital Sign	Age group	Notable criteria	
Heart Rate	<12 years	>130 bpm or increase of ≥ 15 bpm from baseline Or	
		<70 bpm or decrease of ≥ 15 bpm from baseline	
	≥ 12 years	>120 bpm or increase of ≥ 15 bpm from baseline Or	
		<50 bpm or decrease of ≥ 15 bpm from baseline	
Systolic Blood Pressure	<12 years	≥ 125 mmHg or increase of ≥ 20 mmHg from baseline Or	
		≤ 70 mmHg or decrease of ≥ 20 mmHg from baseline	
	≥ 12 to <18 years	≥ 160 mmHg or increase of ≥ 20 mmHg from baseline Or	
		≤ 90 mmHg or decrease of ≥ 20 mmHg from baseline	
	≥ 18 years	≥ 180 mmHg or increase of ≥ 20 mmHg from baseline or	
		≤ 90 mmHg or decrease of ≥ 20 mmHg from baseline	
	Diastolic Blood Pressure	<12 years	≥ 85 mmHg or increase of ≥ 15 mmHg from baseline Or
			≤ 50 mmHg or decrease of ≥ 15 mmHg from baseline
≥ 12 to <18 years		≥ 95 mmHg or increase of ≥ 15 mmHg from baseline Or	
		≤ 50 mmHg or decrease of ≥ 15 mmHg from baseline	
≥ 18 years		≥ 105 mmHg or increase of ≥ 15 mmHg from baseline Or	
		≤ 50 mmHg or decrease of ≥ 15 mmHg from baseline	
Temperature		>38.3 °C or an absolute change ≥ 1.1 °C from baseline	

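### Restart-dose monitoring data are taken out of the routine tables, but no table in SAP 6.7.4 counts notable vital signs or ECG findings at restarts

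*SAP*

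**What the plan says.** **Collection.** Protocol Appendix 2 states: "The same monitoring procedure applies also to the re-initiation of study drug after interruption", and it also covers individual dose increases. SAP 6.7.1 has hourly pulse and blood pressure collected at the first dose, second dose, dose increase and restart. SAP 6.7.2 lists the same occasions for ECGs, including "dose increase (if applicable), and restarting of dose after interruption (if applicable".

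**Removal from routine tables.** SAP 3.8.4.2 says the visit windows for vital signs, ECG and other safety data will "not be applied to any data related to the first dose or second dose or restart dose monitoring which will be summarized separately". SAP 6.4.3 opens its list of routine vital-sign tables, notable abnormalities included, with "The following summaries will exclude hourly vital sign data from the first dose or second dose or restart dose monitoring". Neither sentence names dose increases.

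**The separate summaries.** SAP 6.7.4 gives two outputs all four occasions: hourly vital-sign statistics and the overall monitoring experience. Others stop at the second dose, for example "Incidence of notable vital sign abnormalities based on the notable criteria in Table 6-1 (1st dose and 2nd dose" and "Frequency (%) distribution of ECG findings by ECG evaluation type by time point during 1st and 2nd dose administration". The bradycardia outputs do too: "Incidence of bradycardia events (1st dose and 2nd dose" and "Incidence of bradycardia symptoms by SOC, PT, and severity (1st and 2nd dose".

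**The concern.** The SAP removes restart readings from one set of tables on the promise of another set, and the second set does not contain them for four outputs. The omission falls on an occasion the protocol singles out. Protocol 1.1 lists bradyarrhythmia on restarting after an interruption of more than 14 days as a safety area of note. Protocol 5.5.5 warns that heart-rate and atrioventricular conduction effects may come back on reintroduction, and so applies the initial-dosing procedures. Protocol 9.5.3 plans the incidence of post-baseline notable vital-sign abnormalities without exempting restarts. If the SAP is programmed as written, that incidence leaves out hourly restart readings, and the ECG-findings tables leave out restart ECGs.

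**Working it through.** No figure is involved; the check is where a restart reading can be tabulated.

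**Step 1. Scope of the ten tabular outputs in SAP 6.7.4.**

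| Output | Occasions covered |
|---|---|
| Hourly vital-sign statistics | 1st, 2nd, increase, restart |
| Overall monitoring experience | 1st, 2nd, increase, restart |
| Categorized sitting pulse | 1st only |
| Bradycardia events; medications; symptoms (3 outputs) | 1st, 2nd |
| Notable vital signs | 1st, 2nd |
| ECG parameters by time point | 1st, 2nd |
| Abnormal QTc at dosing | 1st, 2nd |
| ECG findings by time point | 1st, 2nd |

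Count: 2 + 1 + 3 + 4 = 10. Both scopes occur in one list, so the narrower one cannot be read as including restarts. SAP 3.8.4.3 agrees: it extends the vital-sign time points to dose increase and restart, but the ECG time points only to the second dose.

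**Step 2. Where a restart reading could otherwise be counted.**

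- *Notable vital signs:* the routine table in 6.4.3 excludes hourly restart data. No other table counts patients against the criteria.
- *ECG findings and ECG intervals:* the routine tables in 6.6.4 are by visit, and 3.8.4.2 keeps restart monitoring out of the windows. No table remains.
- *QTc:* the overall incidence in 6.6.4 is not by visit and takes all scheduled and unscheduled data. A restart value can enter it, but is not identified as a restart value.
- *Bradycardia events, medications and symptoms:* SAP 6.7.1 describes collection only for first- and second-dose monitoring. Collection text and table scope agree, so no promised summary is shown to be missing.

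**Step 3. Dose increases.** They are not named in the exclusions of 3.8.4.2 and 6.4.3, so read literally their readings stay in the routine tables. SAP 3.8.6, however, exempts dose-increase monitoring, along with the other three occasions, from the rule for choosing one value per window. The readings are thus neither clearly in nor clearly out.

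**Step 4. Do the remaining tables replace the missing counts?**

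- *Hourly statistics:* SAP section 2 includes minimum and maximum, so the lowest pulse at each hour is shown. A minimum is not a count, and the criteria in SAP Table 6-1 depend on age: below 70 bpm under 12 years, below 50 bpm from 12 years.
- *Monitoring experience:* Protocol Appendix 2 lets a child under 12 leave at 60 bpm or more, other criteria being met. A discharge pulse from 60 to below 70 bpm is therefore notable without blocking discharge. From 12 years the discharge limit is 55 bpm. A fall of 15 bpm is notable, and from a baseline of 70 bpm or more it leaves at least 70 − 15 = 55 bpm. Such patients need not appear under any yes/no item.
- *Adverse-event tables:* under Protocol 7.1 an abnormal test result is an adverse event only if it causes signs or symptoms, is clinically significant or needs therapy.

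**The case against.** The strongest reply is that 6.7.4 reflects a deliberate and harmless scope choice. SAP 3.8.4.3 and 6.7.1 are consistent with it. The hourly table shows extremes at restarts. The monitoring-experience table covers all four occasions and records extended monitoring, hospitalization, permanent discontinuation and SAEs. Under Protocol Appendix 2 a low 6-hour heart rate, symptoms, treatment for bradycardia or new significant ECG changes block discharge, and the more serious of these require an overnight stay. New Mobitz II or complete block means permanent discontinuation. Many serious cases would therefore surface in that table. All safety data are listed, the 6.7.4 list is introduced by a word that permits additions, and for rare, non-randomized occasions a listing may serve as well as a sparse table.

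Much of this stands, and it rules out several stronger readings that a reader might infer:

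- *That restart events leave no trace.* The tables and listings above carry part of them.
- *That the hourly table gives only means.* It includes minimum and maximum.
- *That dose increases are also removed from the routine tables.* The exclusions do not name them.
- *That all seven outputs limited to the first and second dose break a promise using data already held.* For the three bradycardia outputs the SAP describes collection only at the first and second dose; the documents do not show that these items are captured at restarts.

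It does not answer the core point. SAP 3.8.4.2 itself promises the separate summary, and neither the extremes nor the yes/no items give patient counts of notable vital signs or ECG findings by arm.

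**Conclusion.** The concern holds for restarts and for four outputs: notable vital signs, ECG parameters by time point, dosing QTc and ECG findings. Patient counts of notable vital signs and ECG findings at restarts have no table; restart ECG intervals have none either. Restart QTc may appear only in the overall table, unattributed. For dose increases the problem is ambiguous placement. For the bradycardia outputs it depends on what the eCRF records.

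This is a safety-table completeness point with no bearing on efficacy. It affects four of ten outputs; how many patients it touches cannot be sized, because the number of restarts is not given. The conclusion assumes that the SAP is followed as written and that the table shells, which are not among the documents, add nothing beyond the list.

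**What to change.** 1. In SAP 6.7.4, give the four outputs the scope already used for hourly vital signs (first dose, second dose, dose increase, restart), reported by arm and type of occasion.
2. In SAP 3.8.4.3, extend the ECG time-point sentence to dose increase and restart, as is already done for vital signs.
3. In SAP 3.8.4.2 and 6.4.3, state whether dose-increase monitoring data are in or out of the routine tables, consistently with 3.8.6, so that each reading is counted once.
4. Check whether the eCRF captures bradycardia events, medications and symptoms at restarts and dose increases. Extend those three outputs and the sentence in 6.7.1 only where it does.

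For the four outputs the cost is SAP wording and re-running planned programs on vital signs and ECGs that 6.7.1 and 6.7.2 say are collected. The downside is a few sparse tables.

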6.8 Pulmonary function tests (PFTs)

Pulmonary function test (PFT) data will consist of the following parameters: FEV₁, FVC, and D_LCO. FEV₁/FVC ratio will be derived based on the FEV₁ and FVC recorded in the database.

6.8.1 Predicted values and units of PFTs

For each subject, the predicted values of the PFT parameters (FEV₁, FVC, FEV₁/FVC, and D_LCO) will be calculated based on the formulas below.

Reference equations (Koopman M, Zanen P, et al (2010) Reference values for paediatric pulmonary function testing: the Utrecht dataset. *Respiratory Medicine*; 105: 15-23) to calculate the predicted values of FEV₁, FVC, FEV₁/FVC

- **Forced expiratory volume in one second (FEV₁) (Unit: Liter/sec):**

Patients <18 years old:

male: $e^{(-1.74+0.016 \cdot \text{height (cm)}+ 0.0017 \cdot \text{age (months)}+ 0.036)}$

female: $e^{(-1.74+0.016 \cdot \text{height (cm)}+ 0.0017 \cdot \text{age (months)})}$

Patients ≥18 years old:

male: $(4.3 \cdot \text{height (m)}) - (0.029 \cdot \text{age (yr)}) - 2.49$

female: $(3.95 \cdot \text{height (m)}) - (0.025 \cdot \text{age (yr)}) - 2.6$

- **Forced vital capacity (FVC) (Unit: Liter):**

Patients <18 years old:

male: $e^{(-11.10+2.37 \cdot \text{Ln}(\text{height (cm)}) + 0.0016 \cdot (\text{age (months)}) - 0.61+0.13 \cdot \text{Ln}(\text{height (cm))})}$

female: $e^{(-11.10+2.37 \cdot \text{Ln}(\text{height (cm)}) + 0.0016 \cdot (\text{age (months)})}$

Patients ≥18 years old:

male: $(5.76 \cdot \text{height (m)}) - (0.026 \cdot \text{age (yr)}) - 4.34$

female: $(4.43 \cdot \text{height (m)}) - (0.026 \cdot \text{age (yr)}) - 2.89$

- **FEV₁/FVC (Unit: %):**

Patients <18 years old:

male: $982.77 - 179.27 \cdot \text{Ln}(\text{height (cm)}) - 177.09 \cdot \text{Ln}(\text{age (months)}) - 2.30$
 $+ 35.57 \cdot \text{Ln}(\text{height (cm)}) \cdot \text{Ln}(\text{age (months)})$

female: $982.77 - 179.27 \cdot \text{Ln}(\text{height (cm)}) - 177.09 \cdot \text{Ln}(\text{age (months)})$
 $+ 35.57 \cdot \text{Ln}(\text{height (cm)}) \cdot \text{Ln}(\text{age (months)})$

Patients ≥18 years old:

male: $-0.18 \cdot \text{age (yr)} + 87.21$

female: $0.19 \cdot \text{age (yr)} + 89.10$

Reference equations to obtain predicted values of DLCO

- **Single breath diffusion capacity (DLCO):**

Patients <18 years old (Unit: mmol/min/kPa):

Male: $e^{(34.80 - 6.89 \cdot \text{Ln}(\text{height (cm)}) - 8.66 \cdot \text{Ln}(\text{age (months)}) + 0.10 + 1.79 \cdot \text{Ln}(\text{height (cm)}) \cdot \text{Ln}(\text{age (months))})}$

Female: $e^{(34.80 - 6.89 \cdot \text{Ln}(\text{height (cm)}) - 8.66 \cdot \text{Ln}(\text{age (months)}) + 1.79 \cdot \text{Ln}(\text{height (cm)}) \cdot \text{Ln}(\text{age (months))})}$

Patients ≥18 years old (Unit: mlCO/min/mmHg):

Male: $(0.3319 \cdot \text{height (cm)}) - (0.1971 \cdot \text{age (yr)}) - 18.006$

Female: $(0.2441 \cdot \text{height (cm)}) - (0.1436 \cdot \text{age (yr)}) - 8.20$

In the above calculations, the height of a subject is from the same visit (if not available, the most recent height measurement prior to or after the visit) when the PFT is conducted and the age should be calculated based on the date when he or she performs the PFTs.

For DLCO, three units may be collected in the eCRFs, which are mlCO/min/torr, mlCO/min/mmHg, and mmol/min/kpa. The PFT tables and listings will use the unit ml/min/mmHg. The other two units will be converted to ml/min/mmHg, prior to any calculations, as follows:

- 1 mlCO/min/torr = 1 mlCO/min/mmHg;
- 1 mmol/min/kpa = 2.986 mlCO/min/mmHg.

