4.1 Inclusion criteria

Core Phase:

Patients eligible for inclusion in this study have to fulfill all of the following criteria:

1. Written informed consent must be obtained before any assessment is performed.

2. Male and female patients aged 10-17 years old*, inclusive (i.e., have not yet had their 18th birthday) at randomization.
3. A diagnosis of MS as defined by the revised consensus definition for pediatric MS, ([Krupp et al 2013](#), [Polman et al 2011](#)).
4. Central review of the diagnosis of pediatric MS will be required for all patients prior to randomization.
5. At least one MS relapse/attack during the previous year or two MS relapses in the previous two years prior to screening or evidence of one or more Gd enhancing lesions on MRI within 6 months prior to randomization (including screening MRI).
6. Expanded Disability Status Scale (EDSS) score of 0 to 5.5, inclusive.

*Exception: If, in a specific country, use of interferon- β -1a IM in children below a certain age is included in the Contraindications section of Avonex (interferon- β -1a IM) local product information, inclusion of such patients is not permitted in that country. E.g. the Russian Avonex product information lists use in children below the age of 12 years as a contraindication.

Fingolimod Extension Phase:

Criterion applies to all patients entering the Extension Phase.

1. Patients that originally met Core Phase Inclusion criteria and completed the Core phase on or off of study drug.

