6.8.3 Data summaries

Summaries on the SAF set by treatment group include:

- Summary statistics and changes from baseline in percent predicted values of PFT parameters by visit
- Number (%) of subjects who had PFT measurements below 80% of predicted by visit
- Shift tables from baseline to lowest post-baseline presenting the frequency of subjects with normal and abnormal (categories are specified in the shell)
- Frequency (%) distribution of relevant pulmonary function test changes (<60% or <80% for any visit or 2 consecutive visits) for percent predicted FEV₁, FVC, and D_LCO

Summaries on the follow-up set include:

- Number (%) of subjects who had PFT measurements below 80% of predicted by time-window (days 1 to 45 after study drug discontinuation and more than 45 days after study drug discontinuation)

The following plots will be provided on the SAF set:

- Box and whisker plot for PFT parameters (percent predicted values) by visit

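### SAP 6.8.1 prints the adult female FEV1/FVC prediction with a rising age slope, against its seven other adult equations; at 18 it is about 5 to 7 points too high

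*SAP*

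**What the plan says.** SAP 6.8.1 gives prediction equations for FEV1, FVC, FEV1/FVC and DLCO, separately for patients under 18 and for those of 18 and over, and states that the predicted values "will be calculated based on the formulas below". The adult FEV1/FVC line for men is -0.18 × age + 87.21. The line for women reads "female: $0.19 \cdot \text{age (yr)} + 89.10", with no minus sign on the age term.

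The adult equations do come into play. Protocol 4.1 admits "Male and female patients aged 10-17 years old*, inclusive (i.e., have not yet had their 18th birthday) at randomization", Protocol 4 allows a Core Phase of up to about two years, and SAP 6.8.1 adds that "the age should be calculated based on the date when he or she performs the PFTs". A girl who turns 18 on study therefore moves to the adult line at her next test.

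SAP 6.8.2 defines percent predicted as the measured value divided by the predicted value, times 100. SAP 6.8.3 then lists "Summary statistics and changes from baseline in percent predicted values of PFT parameters by visit", together with counts below 80% of predicted and shift tables.

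**The concern.** A predicted FEV1/FVC ratio that rises through adult life in women but falls in men, in adjacent lines with almost equal coefficients (0.19 and 0.18), looks like a lost minus sign. If the program follows the SAP text, the denominator of percent-predicted FEV1/FVC is too large for every female visit at 18 or over. Those visits would then look worse than the rest of the SAP's adult equations imply. Lung function is a safety topic for fingolimod in this protocol (Protocol 1.1), so a wrong reference line in the safety tables should be removed even if few patients reach it.

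**Working it through.** The documents give no worked predicted value to reproduce, so the check evaluates the SAP's own equations. Height is not given; 165 cm is assumed, with a range of 145 to 180 cm for females.

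**1. Sign of the age term in the eight adult equations (SAP 6.8.1).**

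| Parameter | Male | Female |
|---|---|---|
| FEV1 | -0.029 | -0.025 |
| FVC | -0.026 | -0.026 |
| FEV1/FVC | -0.18 | **+0.19** |
| DLCO | -0.1971 | -0.1436 |

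Seven fall with age and one rises.

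**2. Ratio implied by the SAP's adult female FEV1 and FVC equations, 165 cm.**

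- Age 18: FEV1 = 3.95 × 1.65 - 0.025 × 18 - 2.6 = 3.4675. FVC = 4.43 × 1.65 - 0.026 × 18 - 2.89 = 3.9515. Ratio = 87.75%.
- Age 20: FEV1 = 3.4175, FVC = 3.8995, ratio = 87.64%.
- Slope: about -0.056 points per year. It is negative at every height tested, from -0.076 at 145 cm to -0.047 at 180 cm.

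**3. Printed line against two alternatives.**

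| Age | Printed (+0.19) | With -0.19 | Difference |
|---|---|---|---|
| 18 | 92.52 | 85.68 | 6.84 |
| 19 | 92.71 | 85.49 | 7.22 |
| 20 | 92.90 | 85.30 | 7.60 |

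Against the implied ratio at 18, the excess is 92.52 - 87.75 = 4.77 points at 165 cm, and 4.6 to 5.2 points over 145 to 180 cm.

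**4. Sex gap at 18.** The adult male line gives -0.18 × 18 + 87.21 = 83.97. The gap is 92.52 - 83.97 = 8.55 points as printed, and 85.68 - 83.97 = 1.71 with -0.19. In the SAP's under-18 equations the sexes differ by a constant 2.30 points.

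**5. Range.** The printed line reaches 100% at (100 - 89.10) / 0.19 = 57.4 years. That age is far outside the trial. But FEV1 is part of FVC, so a ratio above 100% is impossible and the line cannot be right as an adult equation without an age limit.

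**6. Effect on percent predicted at 18.** The relative understatement is 4.77 / 92.52 = 5.2% against the implied ratio, and 6.84 / 92.52 = 7.4% against -0.19. An observed ratio of 85% becomes 91.9% of predicted as printed, 96.9% with the implied ratio, and 99.2% with -0.19.

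**7. Step at the 18th birthday.** The under-18 female equation at 216 months and 165 cm gives 91.77%. Moving to the adult line changes the prediction by 92.52 - 91.77 = +0.75 points as printed, or 85.68 - 91.77 = -6.09 with -0.19. Over 145 to 180 cm the step is +2.3 to -0.3 as printed and -4.6 to -7.1 with -0.19. Males already have a step of -5.1 to -6.9 (160 to 185 cm).

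**The case against.** **The minus sign may have been lost when the PDF was read.** This is possible: in the same section the under-18 female FVC line, as read, has one closing bracket too few. Against it, the male line directly above and the neighbouring formulas kept their minus signs. Only the original page can settle it.

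**The intended coefficient is not in the documents.** This stands. A reader might take 7 points as the established error, but that figure assumes -0.19. The SAP's own adult female equations support about 5 points, and their slope of about -0.06 per year supports the direction of the correction but not the size of 0.19.

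**A rising ratio is not foreign to the section.** The under-18 ratio equation has coefficient -177.09 + 35.57 × ln(height in cm) on ln(age), so it rises with age above about 145 cm. But that applies to both sexes alike, and does not explain why the adult lines go in opposite directions.

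**The printed sign does not create false changes from baseline.** A reader might infer that it does. Step 7 shows otherwise: baseline is normally on the under-18 equation, and the printed adult line happens to sit close to it. The larger step, about -6 points at 165 cm, appears after correction. A patient with a constant observed ratio of 85% goes from 92.6% to 91.9% of predicted as printed, and from 92.6% to 99.2% after correction.

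**Nor does the sign alone push patients below the 80% limit at 18.** At 165 cm an observed ratio of 72% is already 78.5% of predicted on the under-18 equation (72 / 91.77). It is 77.8% on the printed adult line, which is the same category. Only the corrected line moves it, to 84.0%.

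**Reach is small.** This also stands. One derived ratio is affected, in females tested at 18 or over. The SAP 6.8.3 table of relevant changes below 60% or 80% names only FEV1, FVC and DLCO. The ratio can still enter the general percent-predicted, below-80% and shift tables, because 6.8.1 lists it among the PFT parameters.

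**Conclusion.** The point holds as an error in one formula. As printed, the adult female FEV1/FVC line contradicts the male line, the other six adult equations, and the ratio implied by the SAP's own adult female FEV1 and FVC equations. At 18 the prediction is about 4.8 points too high measured against those equations (165 cm assumed), or 6.8 points if -0.19 was meant. Percent-predicted FEV1/FVC is then understated by roughly 5 to 7% in relative terms at 18. By 20 this is slightly more: (92.90 - 87.64) / 92.90 = 5.7% and 7.60 / 92.90 = 8.2%.

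The conclusion rests on the printed page matching the text as read. The number of females tested at 18 or over is not given, so the effect on group summaries cannot be sized. Other PFT parameters and all efficacy analyses are untouched. Importance is low, but the correction costs almost nothing.

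**What to change.** - Check the adult female FEV1/FVC line on the original SAP page and against its source. The only reference 6.8.1 names for the spirometry equations is, by its title, a paediatric dataset, so the source of the adult equations should be added.
- Once confirmed, correct the sign of the age term in SAP 6.8.1 and in the program before the PFT tables are produced.
- Add a note to the PFT tables that the equation changes at 18 and that the predicted ratio then steps down by about 5 to 7 points, in males already and in females after correction with -0.19. Changes from baseline in percent-predicted FEV1/FVC that cross age 18 should be read with that in mind.

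The cost is one look-up, one character in the SAP and the code, and a footnote.
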